# **1 BACKGROUND AND RATIONALE**

## **1.1 General Introduction**

Haemorrhoids or piles are the most common colorectal condition in the local population. Patients often present with bleeding with bowel movement or anal discomfort, both of which causes significant anxiety and stress. For symptomatic sizeable piles, the treatment of choice still remains the conventional open excision (COH). However, this technique carries with it a significant risk of bleeding and pain immediately after the operation, leading to some period of discomfort for the patients. The laser haemorrhoidoplasty procedure (LAH) has been shown in preliminary studies to have less pain, and less complications compared to COH. This study aims to directly compare these two techniques in a local Asian population.

## **1.2 Rationale and Justification for the Study**

We would be conducting a single-centre RCT simultaneously comparing the conventional open Milligan-Morgan haemorrhoidectomy (COH) and the laser haemorrhoidoplasty procedure (LAH) for the treatment of symptomatic grade II-IV haemorrhoids. Primary outcomes will be post-operative pain while secondary outcomes include post-operative bleeding, readmission and/or reoperations, haemorrhoid-related quality of life (QoL) results and recurrence of symptoms up to a year post procedure.

### **1.2.1 Rationale for the Study Purpose**

Treatment of haemorrhoids have long been associated with significant postoperative pain as well as laden with complications, including bleeding and pelvic sepsis, which usually results in patients' distress and readmission back to hospital. The open Milligan Morgan technique has long been regarded as the gold standard treatment for non-circumferential grade II-IV haemorrhoids.

Newer techniques, including doppler haemorrhoidal dearterialization, has yield mixed results with a high recurrence rate.

Laser haemorrhoidoplasty has recently been studied and have shown promising results which has addressed the problems of the open Milligan-Morgan technique. These preliminary studies have shown a significant decrease in post-operative pain scores, less bleeding risk. There have yet to be any well-designed randomised controlled trial (RCT) looking into the longer-term outcomes of this technique.

### **1.2.2 Rationale for Doses Selected**

NA

### **1.2.3 Rationale for Study Population**

Patients would be recruited if they are:

- a. between 21-70 years old
- b. presents with symptomatic haemorrhoids as evident from clinical assessment
- c. never had any haemorrhoid-related operations performed on them before
- d. fit for general anaesthesia

- e. able to give informed consent
- f. willing to be randomized
- g. willing to fill in post-operative questionnaires and be compliant to follow up

We will be excluding individuals who:

- a. Are pregnant
- b. Are prisoners
- c. Intellectually, mentally or emotionally deemed not able to provide an informed consent and/or are unable to fill up the post-procedure questionnaires/VAS score
- d. Have had previous haemorrhoid procedural treatment before (except Rubber Band Ligation)
- e. Declined endoscopic evaluation
- f. Are on anti-platelets and/or anti-coagulation
- g. Have history of thrombophilia
- h. Are on steroids
- i. Have haemorrhoids which are incidentally found on endoscopy/clinical examination but are asymptomatic from it

#### **1.2.4 Rationale for Study Design**

We would be conducting a single-centre RCT simultaneously comparing the conventional open Milligan-Morgan haemorrhoidectomy (COH) and the laser haemorrhoidoplasty procedure (LAH) for the treatment of symptomatic grade II-IV haemorrhoids. Primary outcomes will be post-operative pain while secondary outcomes include post-operative bleeding, readmission and/or reoperations, haemorrhoid-related quality of life (QoL) results and recurrence of symptoms up to a year post procedure.

This would allow us to study this cohort prospectively while comparing the short- and long-term outcomes of both techniques in parallel.

## **2 HYPOTHESIS AND OBJECTIVES**

### **2.1 Hypothesis**

The study team hypothesize that LAH has significantly less pain and bleeding and better QoL scores at 1- and 3-months post-operatively.

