### **2.3 Secondary Objectives**

- Operative duration
- Incidence of post-operative bleeding
- Incidence of readmission to haemorrhoidectomy/haemorrhoidoplasty related symptoms/condition (pain/pelvic symptoms/bleeding)
- Procedure-related complications (thrombosis, fistulation, incontinence, stenosis)
- Incidence and timing of recurrence of haemorrhoid-related symptoms
- Haemorrhoid-specific QoL questionnaire (Haemorrhoid Severity Score)

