## **4 STUDY DESIGN**

This is a single-center, double-blind randomized controlled trial to be conducted in Sengkang General Hospital.

All patients presenting to the clinic or admitted for symptomatic haemorrhoids would be assessed for recruitment.

Figure 1 shows the enrolment process of the study population in the trial. Patients will be seen in the

clinic or in the wards for symptomatic haemorrhoids. All these patients would be approached and be introduced to this study but not recruited yet.

Patients older than 40 years-old with no recent colonoscopy (within 5 years) would need to have a colonoscopic evaluation of the colon after the index admission/clinic visit.

Those younger than 40 would be advised to have a rigid sigmoidoscopy on the day of the operation during the examination under anaesthesia. Only after agreement to the above, the patient would be recruited into the study. They would then be educated on the peri-operative questionnaire separately by a research administrator after recruitment into the trial.

The peri-operative package is split into pre- and post-operative components and will include basic demographics, baseline haemorrhoid-specific QoL questionnaires, VAS scales for POD0-10 and details of the intraoperative procedure and intraoperative description of the haemorrhoids.

Patients who fit the inclusion and exclusion criteria would be recruited into the study. We will perform a 1:1, block-of-4 randomization using a computer-generated programme performed by an independent research administrator who is not part of the surgical team.

They will be allocated only after they are examined under anaesthesia. Allocation is provided in a concealed opaque envelope that is provided by the research administrator on the day of the operation. Thus, the patient is blinded to the procedure. There will also be no cross-over from one study arm to another.

Potential Difficulties and Alternative Approaches to achieve the aims:

Difficulty of recruitment of patients into the trial may be potentially present especially for a procedure that is new in Singapore. Patient counselling and explanation of the procedure would be important and offering a short video clip of the procedure may be helpful. The procedurists/co-investigators of the study team would also be trained by a regional practitioner of the technique before the initiation of the trial to ensure proficiency for reassurance.

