## 4.3 Study Visits and Procedures

### 4.3.1 Screening Visits and Procedures

Patients will be seen in the clinic or in the wards for symptomatic haemorrhoids. All these patients would be approached and be introduced to this study but not recruited yet.

Figure 2 illustrates the visits commitment throughout the study process. After the completion of surgery, patients typically would already have a follow up appointment at 4-6 weeks after the procedure. The clinician will assess the patients progress and examining them for any complications. If their recovery is smooth, most of these patients would be discharged from follow up. During the same setting, the research administrators would collect back the peri-operative package from the patient.

Research administrators would then conduct a phone interview with the patients at 3-month and 1-year after surgery to perform the QoL survey and also looking out for late-onset complications and recurrence of symptoms. If present, they will be offered to have an appointment booked with their primary surgeon. Patients would be informed of the allocation at the clinic review at 4-6 weeks. As none of the visits are outside of normal practice, no remuneration is required.

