## **6.5 Blinding**

Patients will be allocated only after they are examined under anaesthesia. Allocation is provided in a concealed opaque enveloped that is provided by the research administrator on the day of the operation. Thus, the patient is blinded to the procedure. There will also be no cross-over from one study arm to another.

An independent research administrator would conduct a phone interview with the patients at 3-month and 1-year after surgery to perform the QoL survey and also looking out for late-onset complications and recurrence of symptoms. If present, they will be offered to have an appointment booked with their primary surgeon. Patients would be informed of the allocation at the clinic review at 4-6 weeks.

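### The hypothesis names quality of life at 1 and 3 months, but the protocol text describes no 1-month assessment, and both post-operative surveys it does describe follow disclosure of allocation to the patient

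*Protocol*

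**What the plan says.** Section 2.1 hypothesises less pain and bleeding with the laser procedure and "better QoL scores at 1- and 3-months post-operatively". Section 2.3 lists the Haemorrhoid Severity Score as the QoL instrument, without a time point.

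QoL collection is described in two places. Section 4 puts "baseline haemorrhoid-specific QoL questionnaires" in the peri-operative package, together with the daily pain scales for days 0 to 10. Section 4.3.1 provides for a "phone interview with the patients at 3-month and 1-year after surgery to perform the QoL survey", and Section 6.5 repeats these two times and assigns the call to an independent research administrator.

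The clinic visit nearest to 1 month is the review at 4-6 weeks. Section 4.3.1 gives its content: "The clinician will assess the patients progress and examining them for any complications", and "the research administrators would collect back the peri-operative package from the patient". On blinding, the same section says: "Patients would be informed of the allocation at the clinic review at 4-6 weeks". Section 6.5 says the same. Section 4 calls the trial double-blind.

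**The concern.** There are two linked problems.

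First, the hypothesis and the described schedule do not match. The text does not say where the 1-month QoL score comes from. If no form is given at about that time, the data cannot be recovered later. This concerns data collection, so a statistical analysis plan could not repair it.

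Second, the patient is the rater of QoL, and knowing which operation was done can colour the answers. One arm receives a newer technique, and Section 2.4.2 presents it as possibly less painful and less likely to bleed. Section 4 itself warns that QoL measures are subjective and open to recall and interviewer bias. Its remedies are instruction in the pain scale and trained interviewers, and neither deals with a patient who knows the allocation. At stake is how far a QoL difference at 3 months can be credited to the procedure.

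**Working it through.** No sample-size or power figure is involved. The sample size in Section 9.1 rests on the pain score alone. The check is a comparison of the schedule statements.

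**Step 1: time points set side by side.**

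| Time | In the hypothesis (2.1) | QoL collection described in the text | Patient's knowledge of allocation |
|---|---|---|---|
| Baseline | no | yes, package (4) | not yet randomised |
| About 1 month (4-6-week review) | yes (1 month) | none described (4.3.1) | disclosed at this visit |
| 3 months | yes | yes, telephone (4.3.1, 6.5) | known |
| 1 year | no | yes, telephone (4.3.1, 6.5) | known |

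The hypothesised set is {1 month, 3 months} and the described post-operative set is {3 months, 1 year}. They share only 3 months, so 1 of the 2 hypothesised time points has no described collection. The 1-year survey is outside the hypothesis, but it fits the one-year follow-up of secondary outcomes in Sections 1.2 and 1.2.4.

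**Step 2: does the 4-6-week visit fill the gap?** Section 4.3.1 names three things at that visit: clinical assessment with examination, return of the package, and disclosure of allocation. It attaches the QoL survey to the later calls. Sections 4.1 and 4.3.4 repeat those call times and add no earlier contact.

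**Step 3: timing against disclosure.** Disclosure falls at 4 × 7 = 28 to 6 × 7 = 42 days. Taking 3 months as about 91 days, the first survey comes 91 − 42 = 49 to 91 − 28 = 63 days after disclosure, or 7 to 9 weeks. Taking 1 year as 365 days, the second comes 365 − 42 = 323 to 365 − 28 = 337 days after. Both described post-operative surveys (2 of 2) follow disclosure.

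**Step 4: does the independent caller restore blinding?** No. Section 4.1 makes the caller independent of the randomisation process. That may limit interviewer influence, but the text does not say that the caller is blinded, and the respondent knows the allocation in any case.

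**Step 5: reach.** The primary outcome (Section 2.2) is the daily pain score over the first 10 days. It is complete before day 28, so neither problem touches it.

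**The case against.** The strongest reply is that the two items that would settle the first problem are not at hand. Figure 2, the timeline, is not shown, and Appendix 2, the post-procedure questionnaire package, is attached separately. Section 4 says what the package will include and does not present the list as complete. It also says that the package has a post-operative part. Section 3.3 requires willingness to fill in questionnaires after the operation, and Section 3.4 names such questionnaires alongside the pain score. That wording fits paper forms better than telephone interviews. The package comes back at 4-6 weeks, close to the hypothesised 1 month. A 1-month QoL form is therefore plausible, and if it were completed before the visit it would precede disclosure.

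This stands, and it limits the point. A reader might infer that the 1-month claim cannot be tested, or that no QoL at all is collected after surgery while patients are blinded. The documents support neither statement, because both require that the unseen figure and appendix contain no such form.

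It is also fair to say that the protocol states the time of disclosure openly, that QoL is the last of six secondary objectives, and that the 3-month survey is scheduled as hypothesised.

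The reply does not remove the rest. The text of Sections 4 and 4.3.1 places no QoL form at 1 month. If one exists, the text does not say whether it is completed before or after disclosure at the same visit. Whatever the appendix holds, the hypothesised 3-month comparison comes after patients know their allocation.

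**Conclusion.** The point holds in a limited form.

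- **Certain from the text:** the 3-month and 1-year QoL surveys follow disclosure to the patient, so the 3-month comparison named in the hypothesis is not blinded at the level of the rater, although the trial is called double-blind.
- **Certain from the text:** the hypothesis names a 1-month QoL score, and the protocol text describes no assessment that would supply it.
- **Open:** whether Figure 2 or Appendix 2 supplies that assessment. The conclusion is that it is not described, which is weaker than saying that it does not exist.

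The consequence is confined to a secondary outcome. The primary pain comparison and the sample size are unchanged. The change is still worth making, because an early QoL measurement taken before disclosure cannot be obtained afterwards.

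**What to change.** 1. Check Figure 2 and Appendix 2. If they hold a QoL form for about 1 month, say so in Sections 4 and 4.3.1 and state that it is completed before allocation is disclosed.
2. If they do not, add the Haemorrhoid Severity Score to the existing 4-6-week visit, given by the research administrators who already collect the package there. State in Sections 4.3.1 and 6.5 that it is completed before disclosure.
3. Reword the QoL time points in Section 2.1 to 4-6 weeks and 3 months, and give the assessment times in Section 2.3.
4. State that the 3-month and 1-year QoL results are collected after patient unblinding, and report them as such.

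The cost is one short extra questionnaire at a visit that already takes place, plus wording changes. No extra visit or staff is needed.

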### **2.2 Primary Objectives**

Daily visual analogue pain scale (VAS) in the first 10 days after surgery.

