## **3 STUDY POPULATION**

### **3.1 List the Number and Nature of Subjects to be Enrolled**

Based on previous studies, as well as unpublished results from surgeons who have performed LAH around the South East Asian region, we are expecting 50% of the patients in the COH arm to have a VAS score of more than 7.5. We expect to see 25% patients in the LAH arm having a VAS score of more than 7.5.

With a power of 80%, chance of type 1 error (alpha) less than 5% and accounting for 10% of loss to follow up rate, the sample size required for the study to be adequate powered is having 64 patients in

each arm (N=128).

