## **9 SAMPLE SIZE AND STATISTICAL METHODS**

### **9.1 Determination of Sample Size**

Based on previous studies, as well as unpublished results from surgeons who have performed LAH around the South East Asian region, we are expecting 50% of the patients in the COH arm to have a VAS score of more than 7.5. We expect to see 25% patients in the LAH arm having a VAS score of more than 7.5.

With a power of 80%, chance of type 1 error (alpha) less than 5% and accounting for 10% of loss to follow up rate, the sample size required for the study to be adequate powered is having 64 patients in each arm (N=128).

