### **9.2 Statistical and Analytical Plans**

#### **a. General Considerations**

All analysis would be conducted with the assistance or validation of a biostatistician. SPSS or Strata would be used to conduct the analysis. All categorical data would be analysed using the Fisher Exact Test. All continuous variables would be analysed using the Mann-Whitney U test. The level of statistical significance would be set as  $p < 0.05$ .

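### The stated 80% power belongs to the share of patients with VAS above 7.5, not to the stated primary outcome, daily VAS over 10 days, for which no deciding comparison is named

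*Protocol*

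**What the plan says.** **Primary outcome.** Protocol section 2.2 consists of one line: "Daily visual analogue pain scale (VAS) in the first 10 days after surgery". Section 1.2.4 is no more specific: "Primary outcomes will be post-operative pain while secondary outcomes include post-operative bleeding". Section 4 says the VAS is collected from POD0 to POD10, which is 11 possible scores per patient.

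**Hypothesis.** Section 2.1 states that "LAH has significantly less pain and bleeding and better QoL scores at 1- and 3-months post-operatively". It gives no VAS threshold and no time within the first 10 days.

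**Sample size.** Section 9.1 says "we are expecting 50% of the patients in the COH arm to have a VAS score of more than 7.5", and section 3.1, with the same text, adds "We expect to see 25% patients in the LAH arm having a VAS score of more than 7.5". Neither says whether this is the score on a given day, the worst score or a mean. With 80% power, alpha of 5% and "accounting for 10% of loss to follow up rate", the result is 64 per arm (128 in total).

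**Analysis.** Section 9.2 assigns tests by data type only: "All categorical data would be analysed using the Fisher Exact Test" and "All continuous variables would be analysed using the Mann-Whitney U test". It does not say in which form the VAS decides the trial.

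**The concern.** The protocol makes one variable primary and powers another. Daily VAS over 10 days is a set of repeated scores. The share above 7.5 is a single yes/no per patient, and it appears in neither the objectives, the hypothesis nor the analysis section.

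Two things are at stake. First, a reader cannot tell which VAS result would make the trial positive: one day's scores, a mean, the worst score, or the share above a cut. With about ten daily comparisons available, that choice should be fixed before any result is seen, and section 9.2 plans interim looks after 50% and 75% of patients are randomised. Second, the only power statement in the protocol is for a variable that no objective names. Power depends on which variable is chosen and on its test, so the 80% cannot simply be carried over.

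**Working it through.** **1. Reproducing the stated 64 per arm.** Inputs from section 9.1: 50% and 25%, power 80%, alpha 5%, loss 10%. Two-sided testing is assumed, since the section does not say. Pooled two-proportion formula, mean proportion 0.375:

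n = [1.960 × √(2 × 0.375 × 0.625) + 0.842 × √(0.50 × 0.50 + 0.25 × 0.75)]² / 0.25² = 57.7, so 58 per arm.

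Allowing for loss, 58 / 0.9 = 64.4 or 58 × 1.1 = 63.8, against the stated 64. The arithmetic is sound, and it shows that the 80% was calculated for the binary variable.

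**2. If the share above 7.5 is primary.** Evaluable patients: 64 × 0.9 = 57.6, taken as 58 per arm. Power by exact enumeration of all outcomes, 50% against 25%, p < 0.05:

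| Evaluable per arm | Fisher exact | Chi-square, uncorrected |
|---|---|---|
| 58 | 74.3% | 79.9% |
| 62 | 78.3% | 83.4% |
| 64 (no loss) | 80.2% | 84.9% |

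Fisher exact, the test section 9.2 names for categorical data, reaches 80% only if nobody is lost.

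**3. If one continuous VAS score is primary.** The protocol gives no mean difference or SD. If scores on one occasion are normal with equal SDs, its two rates imply a shift of z(0.75) − z(0.50) = 0.674 SD, equivalent to a 0.683 probability that a random open-surgery patient scores higher than a random laser patient. Simulated power of a single Mann-Whitney test:

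| Shift (SD) | Per arm | Power |
|---|---|---|
| 0.674 (implied) | 58 | about 94% |
| 0.674 (implied) | 38 | about 80% |
| 0.5 (assumed) | 58 | about 74% |
| 0.4 (assumed) | 58 | about 55% |

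With whole-number 0–10 scores that keep the 50% and 25% rates, power at 58 per arm stays at about 90–94%.

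**4. If a 10-day mean is primary and the rates describe a single day.** Suppose the 0.674 SD shift is present on k of the 10 days, with equal between-day correlation ρ. The shift of the mean, in its own SDs, is 0.674 × (k/10) / √(ρ + (1 − ρ)/10). At 58 per arm, Mann-Whitney:

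| Days with the shift | Shift of the mean, ρ = 0.9 / 0.7 / 0.5 | Power |
|---|---|---|
| 10 | 0.71 / 0.79 / 0.91 | 96% / 98% / above 99% |
| 7 | 0.49 / 0.55 / 0.64 | 73% / 82% / 91% |
| 5 | 0.35 / 0.39 / 0.45 | 46% / 54% / 66% |

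Normality, k and ρ are assumptions here. The table shows only that the definition of the outcome drives the power.

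**5. If every day were tested separately.** With 10 independent tests at 0.05, the chance of at least one false positive is 1 − 0.95¹⁰ = 40%. With between-day correlation of 0.9 to 0.5, simulation gives about 13% to 36%, depending also on the correlation pattern.

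**The case against.** **A separate SAP may settle the details.** How daily scores are combined and whether POD0 counts are often left to an SAP, and the questionnaire appendix and figures were not available. That is fair for those details taken alone. It does not remove the disagreement between section 2.2 and sections 3.1 and 9.1, because both statements stand in this protocol and would still differ after an SAP chose one.

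**A cut at 7.5 is still the VAS, and sizing on a dichotomy is often conservative.** This is right as far as it goes: with the implied shift on a single score, power is about 94%, above the stated 80%. So no loss of power is shown for the stated outcome. What remains is that the conservative reading holds only for some definitions of the outcome, and the protocol gives none.

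**The low power figures are not the protocol's.** Correct. The 0.5 and 0.4 SD shifts and the 7-day and 5-day scenarios are illustrations and should not be read as a finding that the trial is underpowered.

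**The Fisher shortfall is conditional.** It arises only if the share is primary, and the full 74% figure needs the whole 10% loss to fall on the pain diary. The diary covers POD0–10 and is collected at 4–6 weeks, while follow-up runs to a year, so diary loss could be smaller. Power would then lie between about 74% and 80%. The 74% is what follows from the protocol's own loss figure.

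**The hypothesis is weak evidence.** The 1- and 3-month time points may apply only to quality of life. In that case pain has no time point at all, which leaves the gap unchanged.

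**Conclusion.** The concern holds and must be fixed. The stated primary outcome and the variable behind the sample size differ, and no section links them. The figure of 64 per arm is not miscalculated; its 80% power simply belongs to a variable that is not the stated primary outcome.

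The consequence depends on what was meant. On the binary reading, the protocol's own test and loss figure give about 74%, short of the stated 80%. On the continuous reading, power is about 94% for a single score with the implied shift (normality and equal SDs assumed), and for a multi-day summary it could lie on either side of 80%. Power for daily VAS as written is therefore undetermined, and the direction of any error is unknown. The binary results rest on the protocol's rates and loss with two-sided testing assumed.

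**What to change.** Name one primary variable in section 2.2, state its day or period and whether POD0 counts, and use the same variable in sections 3.1, 9.1 and 9.2. Make day-by-day comparisons supportive. Either of two routes works, with no statistical preference between them:

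- **A. A proportion.** The share with VAS above 7.5 on a named day, or with worst VAS above 7.5 over a stated period, provided the 50% and 25% rates refer to that definition. Then either name the uncorrected chi-square test (about 80% at 58 evaluable per arm) or keep Fisher exact and restate the power as about 74%.
- **B. One score per patient.** For example, mean VAS over a stated period, compared by a single Mann-Whitney test, with its own stated shift, SD and power.

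The cost is wording in these sections and one restated power figure. The daily scores are already collected, and the correction does not itself require enrolment above 64 per arm. The downsides are that day-specific differences become supportive and that the stated power may look less favourable: about 74% under A with Fisher, and dependent on the chosen summary under B. Whether 64 per arm still meets the sponsor's target under B can be judged only once that summary and its shift are stated.
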